5. DATA HANDLING PROCEDURES

5.1 Coding System

AEs and medical history terms will be assigned to a lowest level term (LLT) and a preferred term (PT) and will be classified by high level term (HLT), high level group term (HLGT) and primary system organ class (SOC) according to the MedDRA dictionary, using the most recent version.

Concomitant medications will be classified according to active drug substance using the World Health Organization (WHO) drug dictionary. The generic name, the preferred name and the WHO name will be assigned. In addition, the Anatomical Therapeutic Chemical (ATC) classes will be assigned to the drug ID. ATC codes are defined to the 4th level. For each medication, the primary ATC class will be assigned manually based on the generic name and the reason for use.

5.2 Time-Related Definitions

All assessment dates will be related to the first day of study drug administration. This first day of drug administration is referred to as Day 1. Day -1 is the day that is preceding Day 1 and a Day 0 will not be defined.

The baseline period will be defined as the period from informed consent to the first study drug administration. The baseline value for a variable is defined as the last non-missing value collected before the first study drug administration.

The endpoint value for efficacy variables is defined as the last non-missing value assigned to treatment for the subject. When a patient doesn't recover beyond the study cutoff date, survival duration is stopped at the study cutoff date and it will be regarded as a censored data. The cut-off date will be the end of study (treatment duration maximal 5 days).

All variables planned to be measured at one or more time points and supposed to be time-related will be windowed.

6. ANALYSIS OF SUBJECT SAMPLES

The main subject samples of interest are defined as follows.

The all subjects consented sample will consist of all subjects who:

- Gave their informed consent.

The all subjects <allocated to treatment> sample will consist of all subjects who:

- Were in the all subjects consented sample; and
- Were <allocated to treatment>

The safety sample will consist of all subjects who:

- Were in the all subjects allocated to treatment sample; and
- Had at least one dose of study medication administered.

The full analysis (FA) sample will consist of all subjects who:

- Were included in the safety sample; and

- Had data for at least one post-baseline assessment of any efficacy measurement.

The per-protocol (PP) sample will be defined through blind data review and will consist of all subjects who:

- Were included in the FA sample; and
- Did not present any major protocol violation.

7. DISPOSITION OF PATIENTS AND STUDY COMPLETION

[figure not shown]
The assignment of subjects to subject samples, the disposition of subjects with respect to premature termination, reason for premature termination will be summarized for the treatment group as Table 14.1.1. The flow chart of subject disposition is shown as Figure 7-1.

Data on visit date and the completion status with primary reason for premature termination will be listed in Listing 16.2.1.1.

Individual subject inclusion/ exclusion criteria not met at screening will be listed in Listing 16.2.1.2. Only the exceptions are to be listed, that is, subjects with a response to the inclusion criteria of "No" and/or subjects with a response to the exclusion criteria of "Yes". Subjects with a missing response to inclusion/exclusion criteria will also be presented. Eligibility and assignment will be listed in Listing 16.2.1.3.

All minor and major protocol deviation(s) which judged by principal investigator will be listed in Listing 16.2.2. All subjects who excluded from any of the safety sample, FA sample or PP analysis as well as the reason (s) for exclusion will be listed in Listing 16.2.3.

Figure 7-1 Flow Chart of Subject Disposition

8. DEMOGRAPHICS AND OTHER BASELINE CHARACTERISTICS

Subject demographics and other baseline characteristics will be listed in Listing 16.2.4.1 and Listing 16.2.4.2 and will be summarized as Table 14.1.2.1 using Safety, FA and PP samples. Subgroup analysis of demographics and baseline characteristics by age group (< 24 months old and \geq 24 months old) will be also summarized as Table 14.1.2.2 using Safety, FA and PP samples. Subgroup analysis of demographics and baseline characteristics by weight group (in infants less than 9 kg, in infants from 9 kg to < 13 kg, in children from 13 kg to 27 kg, and in children of more than 27 kg) will be also summarized as Table 14.1.2.3 using Safety, FA and PP samples.

8.1 Medical/ Surgery/ Vaccination History

Any clinical event, including diagnosis, condition, or surgery, that occurred prior to allocation to treatment, is to be recorded on the Medical History form. In case a clinical event concerns a chronic disorder, which means it started in the past and it is still present at the screening visit, it should also be recorded on the Medical History Form. The medical history recorded will be listed by subject in Listing 16.2.4.3. The Medical history, including coding data will be summarized per primary SOC, per HLT by primary SOC and per PT by HLT and primary SOC as Table 14.1.2.4 using Safety sample.

8.2 Concomitant Medication

All medication taken by the subject during the study (from signing the informed consent form through post-study follow-up) is to be recorded on the Concomitant Medication form and will be listed by subject in Listing 16.2.4.4, except for study drug. Concomitant medication, including coding data will be summarized per assigned treatment period for incidence per subject, for primary therapeutic subgroup (the 3rd level ATC code) and for generic name by therapeutic subgroup as Table 14.1.2.5 using Safety Sample.

9. EFFICACY ANALYSIS

FA and PP Samples will be used to all efficacy analysis.

9.1 Primary Efficacy Variable

The primary efficacy variable is the duration (hours) of diarrhea (treatment duration max 5 days). Duration of diarrhea is defined as date and time of the evacuation of the last watery/diarrheal stool before recovery or end of treatment. The duration of diarrhea definition can be referred to Figure 9-1. The primary efficacy parameter, duration of diarrhea, will be analyzed using descriptive

statistics. In addition, a Kaplan-Meier plot will be generated for which summary statistics will be presented as well. The KM algorithm will be applied to derive the median duration (hours) and the 95% confidence intervals for the median, and mean duration. The censored number and event number will be presented as counts and percentage as well.

The SAS code is listed as below:

PROC LIFETEST DATA=duration METHOD=KM PLOTS=SURVIVAL (FAILURE ATRISK); TIME T*status (0); RUN;

[figure not shown]
Note:

[figure not shown]
The proc lifetest analysis will be performed with failure curve (an increasing trend). The duration (hours) of diarrhea or time (hours) until recovery is recorded in the variable T. The variable status is the censoring indicator. A status of 1 indicates an event time, and a status of 0 indicates a censored time. The event is recovery. The censored data are those did not recover during treatment period including drop-outs. When a patient doesn't recover beyond the end of study (treatment duration maximal 5 days), duration is stopped at the end of study date and it will be regarded as a censored data as well. The censored times will be plotted as a plus sign on the Kaplan-Meier.

An event time for the duration of diarrhea is defined as the duration from the date of dosing to the date of the evacuation of last watery/ diarrheal stool before recovery. A censored time for the duration of diarrhea is defined as the duration from the date of dosing to the date of not recovery during treatment period.

An event time for time until recovery is defined as the time from the date of dosing to the date of the evacuation of the first of two consecutive normal stools or no stool within 12 hours after the first normal stool. A censored time for time until recovery is defined as the duration from the date of dosing to the date of not recovery during treatment period.

Individual subject diary card dispensation and subject stool record will be listed in Listing 16.2.6.1 and 16.2.6.2, respectively. The overall duration of diarrhea and additional table of duration of diarrhea for each day of the study will be summarized as Tables 14.2.1 using FA and PP samples. Figures for overall duration of diarrhea can refer to Figure 14.2.1.1 and Figure 14.2.1.2, respectively.

Subgroup analysis of duration (hours) of diarrhea by age group (< 24 months old and \ge 24 months old) will be also summarized as Table 14.2.6 using FA and PP samples. Figures for overall duration of diarrhea by age group can refer to Figure 14.2.6.1 and Figure 14.2.6.2, respectively.

Subgroup analysis of duration (hours) of diarrhea by weight group (in infants less than 9 kg, in infants from 9 kg to < 13 kg, in children from 13 kg to 27 kg, and in children of more than 27 kg) will be also summarized as Table 14.2.11 using FA and PP samples. Figures for overall duration of diarrhea by weight group can refer to Figure 14.2.11.1 and Figure 14.2.11.2, respectively.

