4.3 Time-to-event Endpoints

The time-to-event endpoint will be analyzed by Kaplan-Meier method and presented as mean, median and 95% confidence interval for median.

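### The Kaplan-Meier means of diarrhea duration and time until recovery have no stated restriction time, so if the longest time in a group is censored its mean is cut at the last event and reads too short

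*SAP*

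**What the plan says.** SAP 4.3 makes the mean a standard result: time-to-event endpoints are "presented as mean, median and 95% confidence interval for median". SAP 9.1 repeats this for the primary variable: "The KM algorithm will be applied to derive the median duration (hours) and the 95% confidence intervals for the median, and mean duration". The code given is "PROC LIFETEST DATA=duration METHOD=KM PLOTS=SURVIVAL (FAILURE ATRISK); TIME T*status (0); RUN". It contains no limit for the mean, and no limit is stated elsewhere in the SAP or protocol.

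The code serves two endpoints: "The duration (hours) of diarrhea or time (hours) until recovery is recorded in the variable T". The status rule is "The event is recovery". For the primary duration the event time runs from dosing to the last watery stool before recovery ("An event time for the duration of diarrhea is defined as the duration from the date of dosing to the date of the evacuation of" that stool). On censoring, the SAP says "The censored data are those did not recover during treatment period including drop-outs"; for a child not recovered by the end of the study, "duration is stopped at the end of study date and it will be regarded as a censored data as well".

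Mean time until recovery is a listed secondary result (protocol synopsis and 10.3; SAP 2.2). SAP 9.1 and 9.2.1 repeat both analyses by age group (Table 14.2.6) and weight group (Table 14.2.11). Ordinary descriptive statistics of the duration are also planned, but the SAP does not say how a censored child enters them.

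**The concern.** A Kaplan-Meier mean is the area under the curve of children not yet recovered. That area is closed only if the curve reaches zero. Under the SAP's rule, a child who completes treatment unrecovered is censored at the end of treatment, normally after the last event. This is especially so for the primary duration, whose events are last watery stools and so precede recovery. The curve then stays above zero and the mean depends on where the area is cut.

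With no limit given, the cut falls at the largest event time. The non-recovered child is counted up to that point and not beyond, as if the diarrhea had ended with the slowest recovered child's. The error has one direction, towards shorter diarrhea, and arises only when some children fail to recover. Each age or weight group also gets its own cut, set by its own last event, so the subgroup means need not cover the same span of time.

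**Working it through.** **The plan's own figure.** The only computed figure is the precision in SAP 4.4: 1.96 × √(0.99 × 0.01 / 40) = 0.0308, or 3.1 percentage points. It reproduces. This point does not depend on it.

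**Formula.** With no limit, mean = Σ S(tᵢ₋₁) × (tᵢ − tᵢ₋₁) over event times only, ending at the last event t_last. With a limit L at or beyond t_last, the term S(t_last) × (L − t_last) is added. That term is the shortfall. If nobody is censored before t_last, S(t_last) is the number not recovered divided by n.

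**Inputs from the documents.** n = 40 (SAP 4.4); at least 20 per age group (SAP 3.4); treatment of at most 5 days, nominally 120 h; first dose at noon or evening of Day 1 and last dose on the morning of Day 6 (protocol synopsis, 4.1); recovery within 3 days in the earlier study (SAP 4.4).

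**Assumptions.** Dose times of 12:00 or 20:00 on Day 1 and 08:00 on Day 6 give 116 h for a noon starter and 108 h for an evening starter. Event times are evenly spaced up to 72 h, the counts of non-recovered children are illustrative, and a weight group of 8 is illustrative.

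**One case in full.** Take 36 events at 2, 4, …, 72 h and 4 children censored later. The event times sum to 2 × (36 × 37 / 2) = 1332 h.

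- No limit: (1332 + 4 × 72) / 40 = 40.5 h
- Limit 108 h: (1332 + 4 × 108) / 40 = 44.1 h
- Limit 120 h: (1332 + 4 × 120) / 40 = 45.3 h

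Moving the four censoring times to 73, 96, 120 or 240 h leaves the no-limit mean at 40.5 h.

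**Other cases, last event at 72 h.**

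| n | Not recovered | No limit (h) | To 108 h | To 120 h | Shortfall (h) |
|---|---|---|---|---|---|
| 40 | 0 | 36.9 | 36.9 | 36.9 | 0 |
| 40 | 1 | 37.8 | 38.7 | 39.0 | 0.9 to 1.2 |
| 40 | 2 | 38.7 | 40.5 | 41.1 | 1.8 to 2.4 |
| 40 | 4 | 40.5 | 44.1 | 45.3 | 3.6 to 4.8 |
| 20 | 2 | 41.4 | 45.0 | 46.2 | 3.6 to 4.8 |
| 8 | 1 | 45.0 | 49.5 | 51.0 | 4.5 to 6.0 |

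A later last event shrinks the gap: at 96 h with a limit of 120 h, one of 40 gives (1/40) × 24 = 0.6 h.

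**When it is zero.** If all recover, S(t_last) = 0. The same holds if the non-recovered leave early: with 38 events evenly spaced to 72 h and two children censored at 40 h, the curve reaches zero at 72 h and a limit adds nothing.

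**How likely it is.** Assume exponential recovery times with proportion p recovered by 72 h. The chance that at least one of 40 is unrecovered at 120 h is 1 − [1 − (1 − p)^(120/72)]^40. This is 2% at p = 0.99, 24% at 0.95, 58% at 0.90 and 94% at 0.80.

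**Against sampling error.** For one non-recovered child of 40, counted at 120 h, the standard deviation divided by √40 is 3.9 h, against a shortfall of 1.2 h.

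**The case against.** The strongest reply is that little hangs on this mean. The study is single-arm and descriptive, with no test or success threshold. The Kaplan-Meier analysis supplements the descriptive one, and its only planned confidence interval is for the median, which does not move while more than half recover. Non-recovery is also visible elsewhere: SAP 9.1 reports censored and event counts and marks censored times on the plot, and SAP 9.2.2 gives recovery proportions by day with 95% intervals, overall and by subgroup. At the recovery rate the plan assumes, the problem would seldom arise, and the whole-trial shift is small against sampling error. All of this stands, and it limits the importance of the point.

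It is also fair that the cut at the largest event time is a property of the named procedure, not something the documents state. The printed code has no subgroup statement, so it is not the complete program, and SAP 9.2.1 also refers to a figure that is not reproduced in the text available. What the documents do show is that a mean is required and no limit is given for it.

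A reader might go further and infer that the reported mean will be too short, or that non-recovered children drop out of it. Neither is supported. The shortfall needs a censored longest time, and protocol section 6 provides for stopping early, so some non-recovered children may be censored before the last event. Those who remain still count up to that event.

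**Conclusion.** The gap is real but conditional. When the longest observed time in a group is censored, the planned mean falls below a mean over the treatment period by S(t_last) × (L − t_last). For the whole trial that is roughly 1 h per non-recovered child in 40; it is larger in the age and weight groups, whose means then have different cut-offs. These sizes rest on the assumed event times, non-recovery counts and clock times, and on the procedure's default. 'Too short' is relative to a stated limit, because an unrestricted mean cannot be estimated when the curve stays open.

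A reader might infer that the trial's efficacy conclusion is biased. The documents do not support that: the median, recovery proportions and counts are intact, and no decision rule uses the mean. The point still deserves correction, because mean time until recovery is a listed result and the case in which some children fail should be settled before the data are seen.

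**What to change.** In SAP 4.3 and 9.1, prespecify one restriction time for both endpoints and for all analyses and subgroups, not below any possible event time. The nominal 5 days would serve: add TIMELIM=120 to the PROC LIFETEST statement. If a shorter limit such as 108 h is preferred, truncate T at that limit for every child, because a noon starter could have an event as late as about 116 h on the assumed clock times. Label the result as the mean restricted to the chosen number of hours. Keep the median and its confidence interval as planned.

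The cost is one option and one sentence. The reported mean may be slightly less favourable if some children do not recover. On the assumed clock times, a 120 h limit also carries the curve flat for 4 to 12 h past the last observation of a non-recovered child; for one child of 40 that adds 4/40 = 0.1 h to 12/40 = 0.3 h.

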6 REMOVAL OF SUBJECTS FROM THERAPY OR ASSESSMENT

All subjects are free to withdraw from participation in this study at any time, for any reason, specified or unspecified, and without penalty or loss of benefits to which the subject is otherwise entitled.

The Study Termination form must be completed for all subjects who did not fail screening, those who completed and those who prematurely terminated the study and an end of treatment visit should be performed.

In case of premature termination of the subject from the study, the primary reason for this premature termination is to be indicated according to the following definitions:

- Adverse event: discontinuation due to any adverse event (AE) with a corresponding entry reflected on the Adverse Events form in the CRF
- Lack of efficacy: subject fails to respond to the study drug at an acceptable level where the subject or the Investigator feels it is in the best interests of the subject to seek another treatment.
- Lost to follow-up: the subject's parent(s)/caregiver(s)/legal representative(s) fails to return to the study site for scheduled visits and does not respond to telephone or written attempts to contact.
- Withdrew consent: subject's parent(s)/legal representative(s) decides to stop subject's participation in the study for any reason other than an AE, or is unable to complete the study as described in the clinical study protocol (e.g., subject is relocating to another location).
- Administrative: the Sponsor decides to discontinue the study (either at the study site or the entire study), e.g., general safety problems leading the Sponsor to entirely stop the study.
- Protocol violation – anything which is in direct violation of the clinical study protocol (e.g., inclusion/exclusion violation).

Subjects will terminate the study at the discretion of the investigator and will undergo further diagnosis and alternative treatment under the following conditions.

1. If the subject needs alternative treatments or rescue medication which are prohibited concomitant therapies in this study
Any comedication which may interfere with the evaluation of the efficacy parameters of this study should be avoided (see section 7.7).
Subjects who cannot complete the study duration of five days without continuous intake of concomitant medication or who need rescue medication should be withdrawn. The investigator should consult with the CRO/sponsor prior to withdrawal of the subject.

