9.2 Secondary Efficacy Variables

9.2.1 Time until Recovery

Time until recovery is defined as date and time of the evacuation of the first of two consecutive normal stools or no stool within 12 hours *after the first normal stool*. The time until recovery definition and SAS code can be referred to Figure 9-1. The time until recovery and additional table of time until recovery for each day of the study will be summarized using Kaplan-Meier analysis as Tables 14.2.1 using FA and PP samples. Figures for time until recovery at end of treatment can refer to Figure 14.2.1.3 and Figure 14.2.1.4, respectively.

Subgroup analysis of time until recovery by age group (< 24 months old and \geq 24 months old) will be also summarized using Kaplan-Meier analysis as Table 14.2.6 using FA and PP samples. Figures for time until recovery at the end of treatment can refer to Figure 14.2.6.3 and Figure 14.2.6.4, respectively.

Subgroup analysis of time until recovery by weight group (in infants less than 9 kg, in infants from 9 kg to < 13 kg, in children from 13 kg to 27 kg, and in children of more than 27 kg) will be also summarized using Kaplan-Meier analysis as Table 14.2.11 using FA and PP samples. Figures for time until recovery at the end of treatment can refer to Figure 14.2.11.3 and Figure 14.2.11.4, respectively.

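### The SAP does not settle when a drop-out is censored, and no analysis counts withdrawals for treatment failure as not recovered

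*SAP*

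**What the plan says.** SAP 9.1 makes recovery the event and gives status 0 to everyone else: "The censored data are those did not recover during treatment period including drop-outs". It does not distinguish reasons for dropping out.

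The censoring time appears in two forms. SAP 9.1 has "A censored time for the duration of diarrhea is defined as the duration from the date of dosing to the date of not recovery" during the treatment period. SAP 5.2 says that for a child still not recovered beyond the cut-off, "survival duration is stopped at the study cutoff date and it will be regarded as a censored data", with the cut-off at the end of study (at most 5 days). SAP 9.1 also points elsewhere: "The duration of diarrhea definition can be referred to Figure 9-1". That figure was not visible for this review and may say more.

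Time-to-event endpoints are "analyzed by Kaplan-Meier method and presented as mean, median and 95% confidence interval for median" (SAP 4.3). SAP 9.2.1 adds a by-day table: "additional table of time until recovery for each day of the study will be summarized using Kaplan-Meier analysis".

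The primary variable also gets plain descriptive statistics, with Kaplan-Meier in addition. For these, "Duration of diarrhea is defined as date and time of the evacuation of the last watery/diarrheal stool before recovery or end of treatment" (SAP 9.1).

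Protocol 6 lists as a termination reason "Lack of efficacy: subject fails to respond to the study drug at an acceptable level". It also provides for withdrawal, largely at the investigator's discretion, when a child needs rescue or prohibited medication, worsens or needs hospitalization.

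**The concern.** A child withdrawn because the diarrhea is not resolving is not a random loss. Kaplan-Meier censoring at withdrawal treats that child as having the same later chance of recovery as the children who stayed. In a single-arm trial no comparator shares the resulting shift, so the curve, the by-day figures and the mean are read at face value.

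The plain statistics have a related problem. For a child withdrawn on day 2, end of treatment is day 2. If that child is included, a treatment failure enters the mean as a short diarrhea. SAP 9.1 does not say whether non-recovered children are included.

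The visible SAP gives no rule for failures and no sensitivity analysis. Two programmers could follow it and produce different primary curves.

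**Working it through.** **1. The plan's own figure.** SAP 4.4 gives a precision of 3.1 points for 99% recovery with n = 40. The normal-approximation half-width is 1.96 × √(0.99 × 0.01 / 40) = 0.0308, or 3.1 points. It reproduces. It concerns a simple proportion, not the Kaplan-Meier curve.

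**2. Is the censoring time fixed?** SAP 9.1's date of not recovering is not an observable date for a drop-out; it could be withdrawal, the last diary entry or the end of the 5 days. SAP 5.2 gives a cut-off for children not recovered beyond it. SAP 9.1 repeats that cut-off after the drop-out sentence and says such children are censored *as well*, which reads as a second group. The text therefore allows either reading for drop-outs.

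**3. Assumed inputs.** The documents give no recovery distribution and no failure rate. Assumed: 48 children (the recruitment maximum); recovery time lognormal, median 36 h, log-SD 0.5, capped at 112 h; k failures withdrawn uniformly over 12-48 h (early) or 48-96 h (late); horizon 120 h (5 days).

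**4. Hand check, k = 2, early.**
- Recovery by 72 h among stayers: Φ(ln 2 / 0.5) = 91.7%. Mean among stayers, with the cap: 40.6 h. Censoring at withdrawal gives close to these values.
- Held as not recovered: 46/48 × 91.7% = 87.9%; mean to 120 h (46 × 40.6 + 2 × 120) / 48 = 43.9 h; final recovery 46/48 = 95.8%.
- Plain mean with withdrawal times counted as durations (average 30 h): (46 × 40.6 + 2 × 30) / 48 = 40.2 h, slightly below the mean of the recovered children.

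**5. Simulation (2000 trials per row), censored at withdrawal v held to 120 h.**

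| Failures | Withdrawal | 72 h recovery, % | Mean to 120 h, h |
|---|---|---|---|
| 1 | early | 91.5 v 89.7 | 40.8 v 42.2 |
| 1 | late | 90.3 v 89.9 | 41.4 v 42.0 |
| 2 | early | 91.4 v 87.8 | 41.1 v 43.9 |
| 2 | late | 88.6 v 87.8 | 42.6 v 43.9 |
| 4 | early | 91.1 v 84.1 | 41.6 v 47.2 |
| 8 | early | 90.5 v 76.4 | 42.6 v 53.8 |

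The median moves 0 h with two failures and about 2 h with eight. If the mean is taken only to the last event (assumed software behaviour), the held value with two failures is 43.1 h instead of 43.9 h.

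**6. A second recovery pattern.** Take 40 recoveries spread evenly over 3-70 h, in line with the sizing premise of recovery within 3 days, plus k withdrawals at 24 h. For k = 1: 100% v 97.6% at 72 h, mean to 120 h 36.8 v 38.5 h. For k = 2: 100% v 95.2%, 37.0 v 40.5 h. The direction is the same. If withdrawals come after the last recovery, the two curves coincide.

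**7. If failing children recover after withdrawal (k = 2, early).** Values are 72 h recovery and mean to 120 h. Censoring gives 91.4% and 41.0 h in each case; holding gives about 87.9% and 43.9 h.

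| Later recovery rate relative to stayers | True 72 h recovery, % | True mean, h |
|---|---|---|
| 0 | 87.9 | 43.8 |
| 0.25 | 89.5 | 42.5 |
| 0.5 | 90.5 | 41.7 |
| 1 | 91.5 | 41.0 |

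**8. How many failures?** Exact binomial, n = 48. At an assumed 1% failure rate, the chance of at least 1, 2 or 4 is 38%, 8% or 0.1%; at 5% it is 91%, 70% or 22%.

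**The case against.** The strongest reply has four parts.

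- **The bias is conditional.** A reader might infer that the SAP's primary result is biased as planned. The documents do not support that. SAP 5.2 can be read as holding non-recovered children to the cut-off, and Figure 9-1 may settle it. What is established is that the visible text leaves the date open. This stands.
- **Holding failures to 120 h is not simply the right answer.** It asks a different question, and step 7 shows that it can err more. At half the stayers' rate, censoring is off by 0.9 points and 0.7 h, holding by 2.6 points and 2.2 h; at a quarter, the errors are about equal. This stands, so the held analysis should sit beside the censored one and not replace it.
- **Failures are visible elsewhere.** SAP 9.2.2 gives crude recovered proportions with 95% CI, SAP 9.2.3 gives physician-rated success (Protocol 6 asks for an end-of-treatment visit after premature termination), SAP 9.1 gives censored counts, and SAP 7 gives termination reasons. This limits the harm but corrects neither the curve nor the means.
- **The shift is small.** For one or two failures it is within the trial-to-trial SD (about 4 points and 3 h), and the only Kaplan-Meier statistic with a planned interval is the median, which hardly moves. This is fair on size. A systematic shift in one direction is still worth removing when removal is nearly free.

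Two limits on the figures also stand. The SAP's 99% concerns recovery by day 3, so 1% is not a planned failure rate. The lognormal model gives about 92% at 72 h, below that premise, which is why step 6 uses a second pattern.

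**Conclusion.** The point holds in a limited form. Drop-outs get status 0 whatever the reason, their censoring time is not settled in the visible text, and neither document's text has an analysis that treats failing withdrawals as not recovered. With censoring at withdrawal, two early failures make 72 h recovery look about 3.5 points higher, the mean to 120 h about 3 h shorter, and final recovery 100% instead of 95.8%. With one failure, or two late ones, the shift is under about 2 points and 1.5 h. The four- and eight-failure rows show the range; eight would mean that the whole drop-out allowance (48 − 40) failed. All sizes rest on the assumed recovery times and failure counts.

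The plain mean is affected separately, through the definition of duration, and only if non-recovered children are included.

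Weight: minor to moderate; a cheap improvement.

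**What to change.** In SAP 9.1, aligned with SAP 5.2 and Figure 9-1:

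1. State one censoring time for drop-outs: the last diary time.
2. For both time-to-event endpoints, pre-specify an added analysis that keeps withdrawals for lack of efficacy, rescue for diarrhea, or worsening of or hospitalization for the diarrheal illness as not recovered to 120 h. Label it *recovered without withdrawal for failure*. Classify reasons before database lock, using the adverse event term and concomitant medication where the termination form is not specific. Report it beside the censored analysis so that the two bracket the result; the primary quantity stays as it is.
3. Report the Kaplan-Meier mean restricted to 120 h, and label any plain mean, SD or median *recovered children only, n =*.
4. Use all FA children as the denominator in Table 14.2.2. SAP 4.2's default counts only non-missing data, and SAP 9.2.2 names no denominator.

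Cost: a few lines of SAP and program; the data are already collected. Downsides: slightly less favourable figures, a few judgements on withdrawal reason before lock, and an added analysis that over-penalizes children who recover after withdrawal.
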